6.5.8.6 Handling of Dropouts or Missing Data

Missing data will be handled as follows. Missing data for other data points not covered below will be left as missing. Nominal visits for subjects who withdraw will be handled per Section 6.5.8.2.

6.5.8.6.1 Imputation Method for Efficacy Endpoints

The primary analysis will be completed on the FAS with available data per subject, assuming the overall study discontinuation rate is $<5\%$. If the overall study discontinuation rate is $\geq 5\%$ then the primary analysis will be based on the primary imputation methodology as defined Section 6.5.7.3 and the available data analyses will become robustness analyses.

Additionally, robustness analyses will include repeating the primary analysis on the per protocol set (PPS); the FAS imputing missing data using last observation carried forward (LOCF); the FAS imputing missing data using Markov Chain Monte Carlo (MCMC) multiple

imputation methodology under different assumptions of missingness (at random and not at random) each using 30 imputed values.

6.5.8.6.2 Missing Dates

All missing dates for medications or events that occur after randomization will be queried for a date. If no date is obtained, the following imputation rules will apply:

- For start dates, missing months and days will be imputed as “01”, provided this occurs on or after the date of first study drug self-administration. Otherwise, the date or month (as appropriate) of the first self-administration of study drug will be used
- For stop dates, missing months will be imputed as “12” and missing days will be imputed as the last day of the month. If this creates a date after discontinuation/completion, the date of discontinuation/completion will be used

The imputed dates will only be used to classify events, medications, or therapy as treatment emergent or concomitant. Imputed dates will only be used in the table analyses. Listings will display the available date data.

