8 TRIAL METHODS AND PROCEDURES

8.1 Concurrent Medications and Therapies

The use of any concurrent medication, prescription or over-the-counter, is to be recorded on the subject's source document and corresponding eCRF along with the reason the medication was taken. Concurrent or previous medications are to be recorded for 60 days prior to Visit 0. Any physical therapies, or surgeries are to be documented for 6 months prior to Visit 0.

Therapy considered necessary for the subject's welfare that will not interfere with the evaluation of the study medication may be given at the discretion of the Investigator and in consultation with the medical monitor. If there is any question as to whether the medication may interfere, the investigator should contact the medical monitor or sponsor. Whenever possible, medications should be administered in dosages that remain constant throughout the study duration.

Physical therapies such as lid scrubs, lid wipes, warm compresses, systemic antibiotics (such as tetracyclines) and oral supplements for treatment of ocular conditions must be stable within the last 30 days prior to Visit 1 and should be maintained stable throughout the trial. Changes in those therapies or initiation of such therapies should be recorded on the subject's source document and corresponding eCRF.

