6.5.4.3.1 Concomitant Medications

A medication is considered concomitant if the start date is on or after the date of first dose of study drug or if the start date is prior to the first dose of study drug but the end date is after the date of first dose of the study drug. Partial dates will be imputed using the imputation rule specified in section 6.5.8.6.2. If the medication was started prior to first dose of study drug and the stop date is unknown or ongoing, the medication will be considered concomitant. If the start date or stop date is completely missing and it is unclear as to whether the medication is concomitant, the medication will be conservatively assumed as a concomitant medication.

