6.5.8.6.3 Adverse Events

Whether the adverse event occurred after the first dose of study drug, relationship, and severity should not be missing and will be queried for value. If missing data is present, the AE date will be imputed as detailed above, will be assumed to be related to study drug, and will be assumed to be severe.

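### The partial-start-date rule ignores a recorded stop date, so some medications stopped before first dose would be tabulated as concomitant

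*SAP*

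**What the plan says.** SAP 6.5.8.6.2 opens with its scope: "All missing dates for medications or events that occur after randomization will be queried for a date". If the query yields nothing, the missing parts of a start date become 01, "provided this occurs on or after the date of first study drug self-administration". For results that fall earlier: "Otherwise, the date or month (as appropriate) of the first self-administration of study drug will be used". Stop dates have their own rule, but no step compares an imputed start with a recorded stop. The use of the result is limited: "The imputed dates will only be used to classify events, medications, or therapy as treatment emergent or concomitant". Imputed dates enter tables only; listings show the dates as collected.

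SAP 6.5.4.3.1 defines the class: "A medication is considered concomitant if the start date is on or after the date of first dose of study drug". A second limb covers an earlier start with an end after first dose. The section then states: "Partial dates will be imputed using the imputation rule specified in section 6.5.8.6.2", without mentioning randomization. SAP 6.5.4.3.2 repeats this for therapies.

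For adverse events, SAP 6.5.8.6.3 queries whether the event followed first dose and, where data remain missing, says "the AE date will be imputed as detailed above". SAP 6.5.9.1.3 presumes an event with a partial or missing start to be treatment-emergent only where its status is unclear.

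Protocol 8.1 makes pre-treatment records part of the data: "Concurrent or previous medications are to be recorded for 60 days prior to Visit 0".

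**The concern.** For a start on or after first dose, the definition of concomitant needs nothing else; the end date matters only in the second limb. The imputation rule can move a start forward to first dose without asking whether the product had already been stopped. The two together can give a record a start later than its own recorded stop and then count it as used during treatment.

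Such records are foreseeable. Exclusion criterion 15 bars eye drops in the 24 hours before Visit 1, and Protocol 8.2 bars other dry eye treatments from then until the end of the trial. Subjects who used drops must therefore have stopped, and the stop date may be known when the start is only roughly recalled. If these products appear in the ocular concomitant-medication tables (14.1.7.1 to 14.1.7.3), a reader of the study report could take them for prohibited therapy used on treatment. Non-ocular products stopped before dosing would appear in Table 14.1.7.4 in the same way.

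**Working it through.** The plan states no figure on this point, so the check is to apply the rule to records. The first-dose date and the records are illustrative assumptions.

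Let F be first dose (15 June 2020), E the recorded stop, and S the recorded start with missing parts set to 01.

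- If S ≥ F, the start is S.
- If S < F, the wording allows two readings. *Whole-date*: the start becomes F. *Component*: only the missing day or month is taken from F.
- A record is concomitant if start ≥ F, or if start < F and E > F. Every record below has E < F, so the second limb never applies and the imputed start alone decides.

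| Record | Recorded start | Stop E | S | Whole-date reading | Component reading |
|---|---|---|---|---|---|
| A | May 2020, day unknown | 20 May 2020 | 1 May 2020 | 15 June 2020: concomitant | 15 May 2020: not |
| B | 2019, month and day unknown | 10 Mar 2020 | 1 Jan 2019 | 15 June 2020: concomitant | 15 June 2019: not |
| C | June 2020, day unknown | 10 June 2020 | 1 June 2020 | 15 June 2020: concomitant | 15 June 2020: concomitant |
| D | 2020, month and day unknown | 10 Mar 2020 | 1 Jan 2020 | 15 June 2020: concomitant | 15 June 2020: concomitant |

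All four products were stopped before first dose, so the right answer is not concomitant each time. The whole-date reading misclassifies 4 of 4 and the component reading 2 of 4 (C and D). In C the imputed start is 15 − 10 = 5 days after the recorded stop. In D it is 21 + 30 + 31 + 15 = 97 days after.

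The stop in B and D is earlier than the protocol requires to be recorded: 60 days before Visit 0 plus at most 14 days of screening is 74 days before first dose. The result does not depend on this, because E never enters the imputation. An in-window example is first dose 5 October 2020, start 2020 with month and day unknown, stop 1 September 2020. Here S = 1 January 2020 is before first dose, both readings give 5 October 2020, and the start is 29 + 5 = 34 days after the stop. The record is concomitant.

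Two comparisons on records A to D:

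- If the lead-in of 6.5.8.6.2 is enforced, these records did not occur after randomization, the rule does not reach them, and 0 of 4 are misclassified.
- If a stop before first dose is checked first and the known year and month are kept, 0 of 4 are misclassified under either reading.

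For adverse events, take an onset in June 2020 (day unknown) and an end on 10 June 2020. Through 6.5.8.6.3 the onset is placed on 15 June. Under 6.5.9.1.3 nothing is unclear, so the event is not treatment-emergent. The SAP does not say which provision prevails.

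**The case against.** The strongest reply is scope. The lead-in confines the rule to what happens after randomization, and the cross-reference in 6.5.4.3.1 can be read as importing that limit. On that reading no such record is misclassified. This is a fair reading, but not the only one. Section 6.5.4.3.1 refers partial dates to the rule without qualification, in order to decide whether a product was concomitant, and it must classify products started before first dose. If the lead-in governs, the cross-reference points to a rule that does not cover those starts. The two sections need reconciling either way.

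A second reply is that the SAP is deliberately conservative when timing is unclear. For medications, that fallback applies where a date is completely missing and status is unclear. A partial start with a known stop before first dose meets neither condition.

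Three further replies stand and limit the point:

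- Filling only the missing parts is the more natural reading of the date-or-month phrase, and it leaves starts in an earlier known year or month before first dose.
- Whether an adverse event followed first dose is queried separately, and the presumption in 6.5.9.1.3 covers only unclear cases.
- Under SAP 6.5.4.3 therapies are only listed, and listings show collected dates, so the error has no tabular effect there.

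**Conclusion.** Wrong as written, and minor. Followed through 6.5.4.3.1, the rule counts as concomitant a medication with a partial start in the first-dose year (or year and month) and a recorded stop before first dose. This holds under either reading of the date-or-month phrase, unless the lead-in is taken to override the cross-reference. The affected output is descriptive: Tables 14.1.7.1 to 14.1.7.3 for stopped eye drops and Table 14.1.7.4 for non-ocular products.

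A reader might infer more than the documents support:

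- *That every partial start before first dose is overwritten.* This needs the whole-date reading, which replaces a recorded year or month; the text does not clearly say that.
- *That treatment-emergent event counts are wrong.* The separate query and 6.5.9.1.3 give the right answer for an event known to have ended before dosing. What remains is unstated precedence.
- *That stopped drops become protocol deviations or per-protocol exclusions.* SAP 6.5.2 and 6.5.3 base these on collected data and blinded sponsor review, and imputed dates are used only for the concomitant and treatment-emergent classes.
- *That a large share of subjects is affected.* The documents say nothing about how often start dates are partial, so the frequency is unknown and no count is offered.

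The primary and secondary efficacy tests, alpha and power are unaffected.

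**What to change.** Amend SAP 6.5.8.6.2 to state once which records it covers, and have 6.5.4.3.1, 6.5.4.3.2 and 6.5.8.6.3 refer to that text. Then add, in this order:

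1. A record with a recorded stop before first dose is prior, or not treatment-emergent, before any start date is imputed.
2. A known start year and month are kept, and only missing parts are filled.
3. The first-dose date is used only when the known parts match first dose and the stop is not before first dose.
4. An imputed start is never later than the recorded stop.

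This also settles precedence between 6.5.8.6.3 and 6.5.9.1.3 for events with a known end before dosing. The cost is a few lines of SAP text and of date-derivation code before database lock. It needs no new data and has no apparent downside.

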6.5.8.6.3 Adverse Events

Whether the adverse event occurred after the first dose of study drug, relationship, and severity should not be missing and will be queried for value. If missing data is present, the AE date will be imputed as detailed above, will be assumed to be related to study drug, and will be assumed to be severe.

6.5.8.7 Interim Analyses and Data Monitoring

No interim analyses are planned for this trial.

6.5.8.8 Multicenter Studies

No formal by site analyses will be conducted. Analyses by sites for sites with a sufficient number of subjects can be conducted in an adhoc manner to confirm the uniformity of the overall results.

6.5.8.9 Multiple Comparisons/Multiplicity

To control for inflation of type 1 error rate due to multiple hypotheses, the analysis of the two primary endpoints will be conducted in a hierarchical manner.

If both primary endpoints demonstrate statistically significant superiority of NOV03 versus saline at the two-sided alpha = 0.05 level, the following secondary endpoints will be tested hierarchically to maintain an overall two-sided alpha = 0.05.

1. CFB of Dryness Score (VAS) at Day 15
2. CFB in total Corneal Fluorescein Staining (tCFS) (NEI scale) at Day 15

3. CFB of VAS burning/stinging at Day 57
4. CFB in central Corneal Fluorescein Staining (cCFS) (NEI scale) at Day 57

6.5.8.10 Use of an “Efficacy Subset” of Subjects

The primary analysis will be repeated in the PPS with observed data only as sensitivity analysis. Subjects in the PPS will be analyzed as treated.

6.5.8.11 Examination of Subgroups

If imbalances of interest are noted in the demographics and baseline characteristics, ad hoc summaries by subgroup can be produced.

6.5.9 Safety Analyses

All safety analyses will be performed on the SAF. The primary evaluation of safety of the active arm will be against the control arm.

6.5.9.1 Adverse Events

6.5.9.1.1 General Considerations for Analysis of Adverse Events

General considerations for AE summaries and calculations are:

- Multiple events by PT and SOC will be counted once per subject for each treatment
- For summaries by severity, the most severe event will be selected
- For summaries by relationship, the most related event will be selected

6.5.9.1.2 Adverse Event Dictionary

AEs will be coded using MedDRA version 22.1 or higher. Tables and listings will present data at the system organ class and preferred term level.

6.5.9.1.3 Treatment-Emergent Adverse Events

A treatment emergent adverse event (TEAE) is an AE that occurs or worsens after the first dose of trial treatment.

Where an AE is associated with a partially or fully missing start date or time, and it is unclear as to whether the AE is treatment emergent, it will be assumed that it is treatment emergent.

6.5.9.1.4 Adverse Event Severity

All AEs will be categorized as mild, moderate, or severe as directed in the study protocol.

6.5.9.1.5 Relationship of Adverse Events to Study Drug

All AEs will be categorized as related or not related as determined by investigator using these explanations as specified in the study protocol:

- Suspected: A reasonable possibility exists that the investigational product caused the AE
- Not Suspected: A reasonable possibility does not exist that the investigational product caused the AE

6.5.9.1.6 Serious Adverse Events

An AE is considered serious if, in the view of either the investigator, medical monitor or sponsor, it results in any of the following outcomes as specified in the protocol:

- Death
- A life-threatening AE
- Inpatient hospitalization or prolongation of existing hospitalization
- A persistent or significant incapacity or substantial disruption of the ability to conduct normal life functions
- A congenital anomaly/birth defect
- Medically important

6.5.9.1.7 Summaries of Adverse Event

Treatment-emergent AEs will be summarized. Number of subjects or eyes experiencing a TEAE will be summarized by SOC and PT by treatment group and overall. In summary tables, SOC will be presented alphabetically and events within SOC will be presented by decreasing frequency count based on the total column.

Summary tables (number and percentage of subjects) of AEs will be provided by treatment as follows:

- All treatment-emergent AEs by SOC
- All treatment-emergent AEs by SOC and PT
- All treatment-emergent AEs by SOC, PT and maximal severity
- All treatment-emergent AEs by SOC, PT and strongest relationship
- All treatment-emergent AEs by SOC, PT, maximal severity, and strongest relationship
- All serious treatment-emergent AEs by SOC and PT
- All treatment-emergent AEs leading to premature discontinuation of treatment by SOC and PT
- All non-serious treatment-emergent AEs by SOC and PT occurring at the PT level at rates of 1%, 2%, 3%, 4%, and 5% in at least one treatment arm, separately by percentage

Separate summaries will be performed for ocular and non-ocular AEs. Ocular AEs will be summarized at the subject and eye levels, with separate eye level summaries for study and fellow eye.

An overview table will be provided summarizing the number of:

- TEAEs
- Serious TEAEs
- Serious TEAEs by reason for seriousness
- TEAEs leading to premature discontinuation of treatment
- TEAEs by worst severity
- TEAEs by worst relationship
- TEAEs by pattern
- TEAEs by outcome
- TEAEs by action taken
- TEAEs by action taken related to investigational product
- TEAEs in the investigator's opinion that are ongoing and should be recorded as medical history of the NVU-004 study, and TEAEs by body system.

The treatment groups will be compared in regard to safety endpoints descriptively. No inferential comparison will be conducted.

6.5.9.2 Safety Laboratory Values

Safety laboratory tests will not be collected. Urine pregnancy test results will be captured at Visit 0, Visit 1, and Visit 4. Urine pregnancy test results will be included in a listing.

6.5.9.3 Vital Sign Measurements

Vital signs data will not be collected.

6.5.9.4 Other Safety Measurements

Visual acuity, slit-lamp biomicroscopy, dilated fundoscopy, and intraocular pressure will be summarized by treatment group and visit using descriptive statistics in SAF. Changes from baseline will also be summarized where appropriate. For assessments performed by eye, study eye and fellow eye will be summarized separately.

6.5.9.4.1 Visual Acuity

Visual acuity will be performed at screening, Visits 1-4, and early termination. The base logMAR, which is the last line in which a letter is read correctly, and the number of total letter missed up to and including the last line read will be collected on the CRF. The calculated logMAR will be automatically generated by the EDC as base logMAR + (number of total letters missed \times 0.02). Descriptive statistics for the calculated LogMAR Score will be presented for study eye and fellow eye by treatment and overall at baseline and all post-baseline visits in the SAF. Changes from baseline will also be summarized.

6.5.9.4.2 Slit-lamp Biomicroscopy

Biomicroscopy will be performed at screening, Visits 1-4, and early termination. Observations will be graded as Normal, Abnormal Clinically Significant, or Abnormal Not Clinically Significant. Lids, cornea, conjunctiva, anterior chamber, iris and lens will be

examined. If 'Check if no changes since Visit 0' is checked, the results of the tests at Visit 0 will be used for analysis at that timepoint. Listings will display 'No changes since Visit 0'. Descriptive statistics for the grading by each domain will be presented for study eye and fellow eye by treatment and overall at baseline and all post-baseline visits in the SAF. Shifts from baseline indicative of worsening will also be summarized. Worsening is defined as a shift from normal to abnormal not clinically significant, normal to abnormal clinically significant, and abnormal not clinically significant to abnormal clinically significant.

6.5.9.4.3 Dilated Fundoscopy Examination

A dilated fundoscopy examination will be performed during the trial at screening, Visit 4 and early termination. Observations will be graded as Normal, Abnormal CS or Abnormal NCS. Vitreous, retina, macula, choroid and optic nerve will be examined. If 'Check if no changes since Visit 0' is checked, the results of the tests at Visit 0 will be used for analysis at that timepoint. Listings will display 'No changes since Visit 0'. Descriptive statistics for the grading by each domain will be presented for study eye and fellow eye by treatment and overall at baseline and all post-baseline visits in the SAF. Shifts from baseline indicative of worsening will also be summarized. Worsening is defined as a shift from normal to abnormal not clinically significant, normal to abnormal clinically significant, and abnormal not clinically significant to abnormal clinically significant.

6.5.9.4.4 Intraocular Pressure

Intraocular pressure (IOP) will be measured in each eye by contact tonometry by the examiner and the results will be recorded in mmHg at screening, Visit 4 and early termination. A single measurement will be made to obtain a determination of IOP. Descriptive statistics for the IOP measurement will be presented for study eye and fellow eye by treatment and overall at baseline and all post-baseline visits in the SAF. Changes from baseline will also be summarized.

6.5.10 Determination of Sample Size

The statistical hypotheses for the primary endpoint of CFB corneal fluorescein staining (NEI scale) total score at Day 57 are as follows:

H_{01} : The difference, between study eyes treated with NOV03 and study eyes treated with saline, in the mean CFB corneal fluorescein staining (NEI scale) total score at Day 57 = 0.

H_{A1} : The difference, between study eyes treated with NOV03 and study eyes treated with saline, in the mean CFB corneal fluorescein staining (NEI scale) total score at Day 57 \neq 0, with superiority claimed if the difference is less than 0 (NOV03 minus saline).

The statistical hypotheses for the hierarchical primary endpoint of the CFB Dryness Score at Day 57 are as follows:

H_{02} : The difference, between subjects treated with NOV03 and subjects treated with saline, in the mean CFB Dryness Score at Day 57 = 0.

H_{A2} : The difference, between subjects treated with NOV03 and subjects treated with saline, in the mean CFB Dryness Score at Day 57 $\neq 0$, with superiority claimed if the difference is less than 0 (NOV03 minus saline).

Two hundred fifty (250) subjects (study eyes) per treatment group yields 97.9% power to reject H_{01} in favor of H_{A1} and conclude superiority of NOV03 over saline in the mean CFB tCFS score at Day 57 assuming a true difference (NOV03 minus saline) of -1.0, a common standard deviation of 2.8, and a two-sided alpha = 0.05. Two hundred fifty (250) subjects per treatment group yields 97.9% power to reject H_{02} in favor of H_{A2} and conclude superiority of NOV03 over saline in the mean CFB Dryness Score (VAS) at Day 57 assuming a true difference (NOV03 minus saline) of -10, a common standard deviation of 28, and a two-sided alpha = 0.05. Accounting for an assumed 10% subject discontinuation rate, approximately 560 subjects (280 subject each arm) will be randomly assigned to trial treatment such that approximately 250 evaluable participants per arm complete the trial.

Therefore, assuming independence between tCFS score and Dryness Score (VAS), 250 FAS subjects per treatment group at Day 57 yields $97.9\% * 97.9\% = 95.8\%$ power to reject both H_{01} and H_{02} . A positive correlation between these two endpoints would increase the overall power.

